# 7.5.2 Premature termination or suspension of the study or a study site

The study or a study site can be terminated prematurely, or suspended, by the sponsor. Reasons for termination of the study or closure of a study site may include, but are not limited to, the following:

- Subject enrollment is unsatisfactory.
- The risks and benefits of continuing the study have been reassessed, and the risks outweigh any potential benefits.
- The incidence of AEs constitutes a potential health hazard to the subjects.

- New scientific data on NT 201 do not justify a continuation of the study.
- The investigator or study site exhibit serious and/or persistent non-adherence to the clinical study protocol, the Declaration of Helsinki, ICH–GCP, and/or applicable regulatory or clinical requirements.
- The sponsor decides to terminate the study at any time for any other reason (e.g. based on the recommendation of the DMC).
- AESIs of severe intensity that represent respiratory function disorders or swallowing disorders, that are deemed to be related to IP administration, and that last >1 week will trigger premature termination of the study. The threshold for premature study termination is set to at least five of the severe AESIs described above for the first 50 subjects injected. Once 50 or more subjects have been treated in this study the threshold is set to at least 10% of all treated subjects.
- AESI terms related to respiratory function disorders are aspiration, diaphragmatic paralysis, dyspnoea, pneumonia aspiration, respiratory arrest, respiratory depression, and respiratory failure.
- AESI terms related to swallowing disorders are bulbar palsy, multiple cranial nerve palsies, dysphagia, hypoglossal nerve paresis, cranial nerve paresis, cranial nerve paralysis.

Furthermore, the study (or the participation of a study site) may be ended prematurely if the regulatory authority or the IEC/IRB decides to terminate or suspend approval for the study, the study site, or the investigator.

If the study is prematurely terminated or suspended for any reason, the investigator must inform the subjects and/or their legally acceptable representatives and ensure appropriate follow-up treatment. Within the time-frames stipulated in the applicable regulations, the sponsor will promptly inform the investigators, study sites, IEC/IRB and regulatory authorities of the termination or suspension of the study, and will provide reasons for this action.

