## 4.1.3 Toxicological information

Several studies have investigated the potential clinical improvement in drooling after the injection of *Botulinum* toxin type A (BoNT-A). In contrast, only some studies have investigated histological changes of the salivary glands caused by BoNT-A injection. In one study, BoNT-A was injected into rat submandibular salivary glands and the resulting change in structure and function was monitored. Atrophy of glandular cells, decreased size of acinar cells, and reduced granules in acinar cells were observed on histological examination [Teymoortash 2007]. Another study reported salivary gland shrinkage following the injection of BoNT-A into rat salivary glands without histopathological changes [Coskun 2007]. Animal studies in rabbits did not reveal any histological changes three months after 8 U of BoNT-A administration [Gerlinger 2007].

To support the injection of NT 201 into the salivary glands in humans, a chronic toxicity study has been performed in the Sprague-Dawley rat to determine the toxicity of NT 201 following four intra-glandular administrations to the left submandibular salivary gland at eight week intervals at doses of 0, 2, 10 and 40 LDU/kg and to evaluate the possible regression of any toxic signs during an eight week treatment-free period.

Treatment-related mortality occurred at the dose level of 40 LDU/kg in ten males and five females which were found dead or killed moribund a few days after the second, third or fourth injection. Severe clinical signs (noisy/labored breathing, subdued behavior/decreased activity, pilo-erection, slight hypersalivation and red-stained fur) were noted before death or sacrifice. After the histopathological examination, the cause of death or moribund status was considered to be acute bronchopneumonia with presence of alveolar foreign materials. This was probably a consequence of muscular dysfunction in the region surrounding the pharynx/larynx, resulting in inhalation of material from the oral cavity.

Clinical signs such as noisy breathing and red-stained fur were noted mainly during the two weeks following the second to fourth injections in a few surviving animals treated at 40 LDU/kg by the intraglandular route. No relevant clinical signs were seen in animals treated at a level of 2 or 10 LDU/kg.

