A severely reduced food consumption and marked body weight loss were noted in the week following each injection in animals at 40 LDU/kg, leading to a reduced body weight gain throughout the treatment period, partially reversible at the end of the treatment-free period. Similar, but by far less marked, changes in body weight and food consumption were noted in animals given 10 LDU/kg; these recovered by the next injection. Body weight development at 2 LDU/kg was comparable to that in controls.

Changes in clinical pathology variables were observed throughout the study period; these changes were considered to be associated with the reduced food consumption and low body weight of the animals, and the changes resolved by the end of the treatment-free period.

Mean amylase serum activity was slightly lower than controls at all dose levels from the second injection; this was considered to be associated with the pharmacological effect of the test item.

Mean weights of the left (injected) mandibular salivary gland were lower than controls and also lower compared with the weights of the respective contralateral gland in all treated groups. Histopathologically, a treatment-related multifocal acinar atrophy was observed in the left mandibular salivary gland in some animals receiving 40 LDU/kg, accounting for the slightly lower weight of the gland. These treatment-related changes in mandibular glands were probably related to the pharmacological action of NT 201. At the end of the eight week treatment-free period, the mean weight of the left mandibular gland was still slightly lower than that of controls and the right mandibular gland.

Consequently, under the experimental conditions of this study, the 'no observed adverse effect' level was concluded to be 10 LDU/kg. This is around four times the maximum intended clinical dose in the indication with children (2.5 U/kg) or five times the average intended dose in children in this study (2.0 U/kg).

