As this is the first placebo-controlled, randomized pediatric study with NT 201 in this indication, no clear information regarding its expected side effects is available. However,
on the basis of the literature [Reddihough 2010] the following risks of intraglandular *Botulinum* toxin injections could be identified:

Adverse effects relating to trauma at the site of the injection

- Pain (not severe) at the injection site either during the procedure, or because of gland swelling (hours) or hematoma formation (days) following the procedure.
- Hematoma in the peri-glandular region caused by bleeding from the skin or subcutaneous tissue.
- Intra-oral blood caused by intraglandular/transductal bleeding.
- Swelling of the gland caused by bleeding or injection of too large a volume of solution.
- Swallowing problems, caused by swelling of the gland, which usually resolves within two hours.
- Infection.
- Theoretical possibility of trauma to the facial nerve when injecting the parotid gland.

Adverse effects relating to BoNT-A and BoNT-B

- Increased dryness of the mouth leading to problems such as manipulation of solid food.
- Thickening of saliva because the water component is influenced by cholinergic blockade, leading to an increase in the concentrations of mucins and proteins.
- Chewing and swallowing problems because of diffusion of BoNT into the surrounding muscular tissue.
- Loss of BoNT because of intravascular injection (without systemic consequences because of the low dosages used; however, iatrogenic botulism has been reported in a single case).

When BoNT is injected into the parotid, diffusion of BoNT into the masseter muscle is possible, causing weakness in chewing.

Currently no large, randomized, double-blind, placebo controlled clinical trial has been performed on the use of NT 201 in the management of sialorrhea in adult or pediatric patients. Only small case series and clinical trials with significant design limitations have been performed.

Kossmehl [Kossmehl 2007] found in a case series (N = 6) of patients suffering from Parkinson's disease, multiple system atrophy or stroke a clear reduction in saliva production (greater than 50% reduction in saliva production by objective measurement of saliva weight collected with dental rolls before and after placement), and drooling severity and frequency scale [DSFS] score improvements in all patients after ultrasoundguided injections of 50 U NT 201 in both parotid glands (total dose 100 U).

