# 7.4 Eligibility criteria for continued treatment in the extension period

Criteria for the transition to the extension period (V6/6a) and for continued treatment within the extension period (V10/10a and V14/14a) are listed below. (Note that the pairs of visits 6/6a, 10/10a and 14/14a will normally take place on the same respective day.)

If these eligibility criteria are not fulfilled at the end-of-cycle visit postponement of study treatment may take place at the beginning of the following injection cycle of the extension period. The re-injection visit can be postponed for up to a maximum of two weeks (but no longer than 18 weeks after the preceding treatment visit). For subjects who still do not fulfill the eligibility criteria at the revisit, study participation will be ended.

	Eligibility Criteria for Extension Treatment	Ratio- nale	Visits 6, 6a, 10, 10a, 14, 14a
1.	Clinical need for re-injection.	Ind	Х
2.	Absence of medically-relevant severe adverse events of special interest that are judged to have a causal relationship to the study treatment (indicative of toxin spread in the area of injection), especially respiratory arrest/distress/failure and dysphagia necessitating diet changes occurred during any period of the study.	Safety	Х
3.	No concomitant infection or inflammation in the head and neck region.	Safety	Х

Page 52 of 183

		Eligibility Criteria for Extension Treatment	Ratio- nale	Visits 6, 6a, 10, 10a, 14, 14a
4.	Neg fem	ative result of pregnancy test (testing only performed for ale with history of menarche, i.e. the first menstrual bleeding).	Safety	Х
5.	No :	significant risk of suicidality since last injection based on the Investigator's judgment, and	Safety	Х
	•	if appropriate, as indicated by a response of "no" to questions 4 or 5 in the suicidal ideation section of the C-SSRS		
	•	and no non suicidal self-injurious behavior		
	•	and no suicidal behavior.		

Definition of indication for continued study treatment [Ind]; administrative [Adm].

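### The numerical study-stopping trigger in Protocol 7.5.2 gives no weight to a related fatal or life-threatening respiratory or swallowing event that is over within a week

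*Protocol*

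**What the plan says.** Protocol 7.5.2 lists reasons for ending the study early. One is numerical. It covers AESIs of severe intensity on a named list of terms that includes respiratory arrest, respiratory failure, aspiration, aspiration pneumonia and dysphagia, and it applies to those "that are deemed to be related to IP administration, and that last >1 week will trigger premature termination of the study". An event must meet all four conditions: on the list, severe, related, and longer than a week.

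The limit has two limbs. The first is "at least five of the severe AESIs described above for the first 50 subjects injected". The second reads "Once 50 or more subjects have been treated in this study the threshold is set to at least 10% of all treated subjects".

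Two rules for the individual child cover similar events with no duration condition. Section 7.4 bars re-injection after severe related AESIs ("indicative of toxin spread in the area of injection), especially respiratory arrest/distress/failure and dysphagia necessitating diet changes"). Section 7.5.1 ends a child's participation after any severe event on the same list of terms, whether or not it is related.

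The other study-level reasons in 7.5.2 carry no number, and the list is expressly not exhaustive. Section 12.4.7.3 lets the DMC recommend stopping and refers to 7.5.2. SAP 7.7.3 repeats the DMC's possible recommendations and adds no limit.

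**The concern.** A duration condition makes sense for brief procedural effects. Section 4.3 gives an example: "Swallowing problems, caused by swelling of the gland, which usually resolves within two hours". It does not suit the gravest terms on the list. Taking an event to end at death or at recovery, a related respiratory arrest that is fatal on day 2 scores zero, and so does a related respiratory failure reversed in five days. A severe dysphagia lasting eight days scores one. For a safety trigger that order is the wrong way round.

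At stake is the one part of the stopping provisions that does not depend on judgment. The children are recruited in staggered cohorts because caution is needed, and the automatic limit should not be blind to the events that most call for it.

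A lesser matter is the unit. The first limb counts AESIs and the second is a percentage of subjects. The text does not say how several listed terms in one child enter the second limb.

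**Working it through.** **1. The plan's own limits.** 5/50 = 10%, so the two limbs meet at 50 subjects if one AESI equals one child. At 249 treated, 0.10 × 249 = 24.9, so the limit is 25.

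**2. What the wording scores.** All examples are severe, related and on the list.

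| Event | Lasts over one week? | Counts in 7.5.2? | Child affected by 7.4 or 7.5.1? |
|---|---|---|---|
| Dysphagia, 8 days | yes | 1 | yes |
| Respiratory failure, reversed in 5 days | no | 0 | yes |
| Respiratory arrest, fatal on day 2 | no | 0 | not applicable |

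**3. Whether a short fatal course is conceivable.** Protocol 4.1.3 reports rats at 40 LDU/kg "found dead or killed moribund a few days after the second, third or fourth injection". It adds that "the cause of death or moribund status was considered to be acute bronchopneumonia with presence of alveolar foreign materials". The same section sets the no-effect level at 10 LDU/kg: "This is around four times the maximum intended clinical dose in the indication with children". On that scale the lethal dose is 40/2.5 = 16 times the maximum and 40/2.0 = 20 times the average intended dose. No relevant clinical signs were seen at 2 or 10 LDU/kg. This shows that such a course can occur. It says nothing about its frequency in children.

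**4. Size.** The documents give no event rates, so both inputs are assumptions. Let p be the share of children with an event countable under the corrected rule, one event per child. Let g be the share of those events that are fatal or life-threatening and over within a week, which the present rule misses. At a single look at 50 exposed children, the chance of triggering is P(X ≥ 5), with X binomial (50, p(1 − g)).

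| p | corrected rule (g = 0) | present rule, g = 5% | present rule, g = 10% |
|---|---|---|---|
| 10% | 0.57 | 0.52 (rate 9.5%) | 0.47 (rate 9.0%) |
| 15% | 0.89 | 0.86 (rate 14.25%) | 0.82 (rate 13.5%) |

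The expected number of missed events per 50 children is 50pg. It runs from 50 × 0.10 × 0.05 = 0.25 to 50 × 0.15 × 0.10 = 0.75.

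The same formula at 249 children with limit 25 gives 0.99 against 0.98 or 0.96 at p = 15%. At p = 10% it gives 0.52 against 0.42 or 0.31. The last row is sensitive because the assumed rate sits on the limit itself; the events missed there number 249 × 0.10 × g, about 1.2 to 2.5.

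**5. The unit.** Five terms reported in four children (for example dysphagia with aspiration in one of them) meet the first limb. The same four children are 4/50 = 8%, below the second. At 249, a count of children needs 25. A count of events, at an assumed 1.25 to 1.5 terms per affected child, needs 25/1.25 = 20 or 25/1.5 = 16.7, so 17, children. The wording of the second limb most naturally means children, so this calls for a clarification only.

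**The case against.** The strongest reply is that the trigger is a backstop, and that the change would not alter what happens after a death. SAEs and AESIs must be reported within 24 hours (10.2, 10.3). New cohorts open only if the DMC sees no significant risk (6.3). The sponsor may stop for any reason, including DMC advice (7.5.2). Under the fix a single related death would still be one towards a limit of five. All of this stands, and it limits the weight of the point. It does not justify a count that leaves such a death out.

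It is also fair that rules for one child may be stricter than a rule for ending a whole study. The comparison with 7.4 and 7.5.1 therefore shows no contradiction. It shows only that the protocol elsewhere treats these events as grave without asking how long they lasted. The rat deaths are weak evidence for the reason given above, and the charter may already contain a suitable rule.

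Four stronger readings are tempting, and the documents do not support them:

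- **The study could not be stopped after a death.** The list in 7.5.2 is open, and the DMC's reference is to the whole section, so the DMC is not tied to the numerical clause.
- **The duration condition should go altogether.** If half of all severe related events were short, the filter would cut the chance of triggering at a 10% rate from 0.57 to 0.10. That half is invented, and the filter has a proper use for brief procedural events.
- **The first limb should count children.** Counting AESIs is the more protective reading for the earliest subjects. Changing it would make early stopping harder.
- **The denominator should be children exposed to NT 201.** Section 8.5.2 gives the DMC biostatistician only Treatment A and B labels, so this would need actual unblinding.

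**Conclusion.** The point holds in limited form. The only numerical stopping trigger in the protocol or SAP gives no weight to a listed, severe, related event that is fatal, or life-threatening and reversed, within a week. This follows from the wording and rests on one assumption: that an event's duration ends at death or recovery.

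The effect on the chance of triggering cannot be determined from the documents. It is probably small: fewer than one missed event per 50 children in the scenarios shown, all of which rest on assumed rates, one event per child and a single look. The gap is in the automatic count. Discretionary stopping by the DMC and sponsor remains. The statement that this is the only numerical limit does not extend to the DMC charter.

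**What to change.** In Protocol 7.5.2, and in the DMC charter if it does not already do so, state that a listed severe related AESI that is fatal or life-threatening counts whatever its duration, and that the one-week condition applies to all other listed events.

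As a secondary clarification, state that the 10% limb counts children with at least one qualifying event. Leave the five-AESI limb before 50 subjects as it is.

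The cost is two sentences. No extra data are needed: onset, resolution, intensity, relatedness, seriousness and outcome are already recorded (10.1), fatal is an outcome category (10.1.3), and life-threatening is a seriousness criterion (10.2). The downside is that the limit is reached slightly sooner. Acting on a single death stays with the DMC and sponsor, and the level of the limit stays their clinical decision.

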## 7.5 Removal of subjects from treatment or assessment

## 7.5.1 Discontinuation of subject's study participation

In accordance with the Declaration of Helsinki and the informed consent form, the subject or his/her parent(s) may discontinue the subject's participation in the study at any time without any penalty or loss of benefits to which the subject is otherwise entitled (see Section 7.5.3). Both the premature withdrawal from the study and the reason(s) for this are to be recorded in the subject's file and the eCRF. The date and circumstances of the discontinuation should be stated.

Subjects are to be withdrawn from the study by the investigator at any time if any of the following occurs:

- Withdrawal of informed consent.
- Pregnancy (no further administration of NT 201, blood sampling, or any other interventional or invasive procedure will be performed).
- Any AE for which treatment continuation would constitute an unacceptably high risk for the subject.
- Any eligibility criteria for reinjection are not met within 18 weeks after the previous injection of IP in the respective injection cycle (MP or OLEX).

- AESIs of severe intensity that represent respiratory function disorders or swallowing disorders will trigger the premature termination of a subject without reexposition to IP. The terms for these severe AESIs are:
  - AESI terms related to respiratory function disorders are aspiration, diaphragmatic paralysis, dyspnoea, pneumonia aspiration, respiratory arrest, respiratory depression, and respiratory failure.
  - AESI terms related to swallowing disorders are bulbar palsy, multiple cranial nerve palsies, dysphagia, hypoglossal nerve paresis, cranial nerve paresis, cranial nerve paralysis.
- Positive report on suicidality of subject (C-SSRS answer "yes" to questions 4 or 5 or any suicidal behavior) or non-suicidal self-injurious behavior.

Deviations from this clinical study protocol, or conditions arising from the exclusion criteria as set out in Section 7.3, may (but will not necessarily) lead to the subject's withdrawal. All such conditions are to be properly documented. In such cases, the decision on whether or not to withdraw the subject will be made by the investigator in consultation with the sponsor, taking principally the safety of the subject into account.

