# 8.2.6 Treatment of overdose

As study treatment will be administered exclusively in a clinical setting by study-site medical personnel, the risk of overdose (e.g. due to reconstitution or application error) in this study is considered to be low. Nevertheless, any deviation from the planned dosing scheme (excluding dose adjustment due to body weight changes or AEs) is to be reported as an AE and treated accordingly. The investigator is advised to use best clinical judgment in the unlikely event of an overdose with the IP.

There is no significant information regarding overdose from clinical studies in adults in upper limb spasticity, cervical dystonia, and blepharospasm.

Excessive doses of NT 201 may be expected to produce neuromuscular weakness with a variety of symptoms. Signs include acute symmetric, descending flaccid paralysis with prominent bulbar palsies such as diplopia, dysphonia, and dysphagia, which would typically occur 12 to 72 hours after exposure [Arnon 2001]. Furthermore, signs and symptoms of overdose can result in ptosis, generalized muscle weakness and paralysis of respiratory muscle leading to aspiration pneumonia. Clinical cases of iatrogenic botulism after BoNT injection were reported in four adult patients whose clinical signs were consistent with those of naturally occurring botulism [Chertow 2006].

Symptoms of overdose are not immediately apparent following injection. By the time symptoms of intoxication are observed, treatment with anti-toxin will no longer be effective because the neurotoxin has already irreversibly blocked the transmitter release. Compounds releasing acetylcholine (e.g., physostigmine, guanidine, 3,4-diaminopyridine) might be helpful. However, there is no experience with a specific antidote to BoNT including NT 201 in the clinical management of overdose. A published case report describes the successful treatment of dysphagia with intranasal neostigmine [Marchini 1997].

Subjects (if applicable) and parent(s) should be advised to seek immediate medical care if symptoms such as swallowing difficulties, speech or breathing problems occur. Subjects (if applicable) and parent(s) will receive a subject card with contact information in case of emergency (see Section 3.3.3) should additional information on the scope of the study be required.

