#### 10.3 Adverse events of special interest (alert terms)

All AEs of special interest (alert terms) that occur during the study period, whether considered to be related to IP(s) or not, must be reported by telephone, telefax, or secure e-mail within 24 hours of knowledge of the event (see contact details in Section 10.2.)

At each visit the investigator or a representative authorized by the investigator will ask actively the child/adolescent (if applicable) or his/her parent(s)/carer about the occurrence of AESIs.

For this study, the following AEs are defined as AESIs:

MedDRA Preferred Term (MedDRA version 15.1)						
Accommodation disorder	Eyelid ptosis	Peripheral nerve palsy				
Areflexia	Facial paresis	Peripheral paralysis				
Aspiration	Hemiparesis	Pelvic floor muscle weakness				
Botulism	Hypoglossal nerve paresis	Pneumonia aspiration				
Bradycardia	Hyporeflexia	Pupillary reflex impaired				
Bulbar palsy	Hypotonia	Quadriparesis				
Constipation	Ileus paralytic	Respiratory arrest				
Cranial nerve palsies, multiple	Monoparesis	Respiratory depression				
Cranial nerve paralysis	Muscular weakness	Respiratory failure				
Diaphragmatic paralysis	IIIrd nerve paresis	Speech disorder				
Diplopia	IVth nerve paresis	Trigeminal nerve paresis				
Dysarthria	VIIth nerve paralysis	Urinary retention				
Dysphagia	Paralysis	Vision blurred				
Dysphonia	Paralysis flaccid	Vocal cord paralysis				
Dyspnea	Paraparesis	Vocal cord paresis				
Extraocular muscle paresis	Paresis					
Eyelid function disorder	Paresis cranial nerve					

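### The counted terms for the numeric safety stop in Protocol 7.5.2 omit Botulism, so a qualifying case entered only under that diagnosis would not count

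*Protocol*

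**What the plan says.** Protocol 7.5.2 contains a numeric stop. An event qualifies if it is an AESI of severe intensity, is a respiratory function or swallowing disorder, is judged related to the investigational product (IP), and lasts more than one week. On the limit, the section says: "The threshold for premature study termination is set to at least five of the severe AESIs described above for the first 50 subjects injected". From 50 treated subjects onward, the limit becomes 10% of all those treated.

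Two further bullets give the terms. There are seven respiratory terms (aspiration, diaphragmatic paralysis, dyspnoea, pneumonia aspiration, respiratory arrest, respiratory depression, respiratory failure). For the second group: "AESI terms related to swallowing disorders are bulbar palsy, multiple cranial nerve palsies, dysphagia, hypoglossal nerve paresis, cranial nerve paresis, cranial nerve paralysis". Protocol 7.5.1 uses the same 13 terms for withdrawing an individual subject and introduces them with "The terms for these severe AESIs are".

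Table 7 in Protocol 10.3 lists Botulism as an AESI in its own right, and SAP 7.5 (Table 4) keeps it. Section 10.3 makes reporting within 24 hours mandatory for "All AEs of special interest (alert terms) that occur during the study period". Section 10.1 asks the investigator to record the diagnosis or the main symptom.

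Section 8.2.6 describes toxin excess: "Signs include acute symmetric, descending flaccid paralysis with prominent bulbar palsies such as diplopia, dysphonia, and dysphagia", and also ptosis, "generalized muscle weakness and paralysis of respiratory muscle leading to aspiration pneumonia".

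Section 7.5.2 also keeps a discretionary route: "The sponsor decides to terminate the study at any time for any other reason (e.g. based on the recommendation of the DMC").

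**The concern.** The stop protects breathing and swallowing. It counts dysphagia, bulbar palsy, aspiration pneumonia and respiratory failure when each is entered as its own event. It does not count the toxin-spread diagnosis that can bring those same problems together. The protocol treats that diagnosis as foreseeable and grave: section 9.1.1.3 says iatrogenic botulism needs a pediatric intensive-care facility.

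An investigator who makes the diagnosis may enter Botulism alone. That satisfies the diagnosis-or-symptom field in 10.1 and, since Botulism is itself an AESI, arguably also 10.3. No section maps Botulism to a listed term or asks for its components to be entered separately. At stake is the completeness of the one count in the protocol meant to end the study without relying on anyone's discretion.

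**Working it through.** **1. Term check.** The respiratory list has 7 terms and the swallowing list 6, so 7 + 6 = 13. Table 7 prints 49 preferred terms. All 13 have a counterpart there (allowing for spelling and word order). Botulism is one of the 49 and none of the 13.

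**2. Overlap with the picture in 8.2.6.**

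| Feature in 8.2.6 | Counterpart among the 13 |
|---|---|
| Bulbar palsy | yes |
| Dysphagia | yes |
| Respiratory-muscle paralysis | yes (e.g. diaphragmatic paralysis, respiratory failure) |
| Aspiration pneumonia | yes |
| Diplopia, dysphonia, ptosis, generalized weakness | no |

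The overlap is partial. The parts that bear on breathing and swallowing are counted; the diagnosis is not.

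**3. The plan's own limit.** 5/50 = 10%, which agrees with the later 10% rule. For larger numbers the limit is 10% of N, rounded up: 6 at N = 60, 9 at N = 90, 25 at N = 249.

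**4. Effect of one uncounted case.** This needs no assumption about rates. It changes the decision only when the true count is exactly at the limit.

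| Treated | True count (stop) | Literal count (no stop) |
|---|---|---|
| 50 | 5 (10%) | 4 (8.0%) |
| 60 | 6 (10%) | 5 (8.3%) |
| 90 | 9 (10%) | 8 (8.9%) |
| 249 | 25 (10.04%) | 24 (9.6%) |

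**5. How often this could matter in the first 50.** The documents give neither the rate p of qualifying cases nor the share s entered only as Botulism. Both are assumptions, with one qualifying event per subject. True count X ~ Bin(50, p); literal count X' ~ Bin(50, p(1 − s)). The loss is P(X ≥ 5) − P(X' ≥ 5).

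| p | P(X ≥ 5) | P(X = 5) | Loss, s = 1% | Loss, s = 5% |
|---|---|---|---|---|
| 2% | 0.0032 | 0.0027 | 0.0001 | 0.0006 |
| 5% | 0.1036 | 0.0658 | 0.0033 | 0.0158 |
| 10% | 0.5688 | 0.1849 | 0.0093 | 0.0473 |

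In percentage points the loss is 0.01, 0.3 and 0.9 at s = 1%, and 0.06, 1.6 and 4.7 at s = 5%. At p = 5% and s = 1%, the expected number of Botulism-only cases is 50 × 0.05 × 0.01 = 0.025 per 50 children.

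The low end is the more plausible. Section 4.3 mentions a single reported case of iatrogenic botulism with this type of injection. Section 8.2.6 adds: "Clinical cases of iatrogenic botulism after BoNT injection were reported in four adult patients". The reference list shows those four followed an unlicensed, highly concentrated preparation, so they say little about this trial's doses.

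**6. Does the same omission matter in 7.5.1?** Re-injection criterion 2 in 7.4 requires that no medically relevant, severe, causally related AESI has occurred in any period of the study. It is not tied to the 13 terms, and once failed it cannot be regained. Section 7.5.1 separately makes withdrawal mandatory when any re-injection criterion is not met within 18 weeks. Together these already force withdrawal for medically relevant, severe, related botulism, so adding the term to 7.5.1 gains almost nothing.

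**The case against.** The strongest reply is that the gap opens only if reporting falls short. Dysphagia, aspiration, bulbar palsy and respiratory failure are each AESIs, all AESIs must be reported, and families are asked about them at every visit after an injection. A child with a week of severe swallowing or respiratory trouble should therefore have a listed term on file. This largely stands, and it is why the effect is small. It does not close the gap, because no section requires component entry once a diagnosis has been made.

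Second, the lead sentence of the stop is functional: it speaks of events that represent respiratory or swallowing disorders, and botulism with such involvement fits those words. The reasons in 7.5.2 are also introduced as non-exhaustive. That reading is possible, but the two bullets that follow enumerate terms. If the count depends on which sentence is given priority, the text needs clarifying.

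Third, a qualifier that asks only for respiratory or swallowing involvement would let severe botulism with mild or brief dysphagia count, which goes beyond the rule. This succeeds, and the fix is worded to meet it.

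A reader might infer that the plan leaves a child with botulism open to re-exposure, or the study unable to stop. The documents support neither. Re-exposure is blocked by 7.4 criterion 2 with the re-injection bullet in 7.5.1. A case needing hospital care would be a serious event under 10.2. The DMC reviews AESIs and serious events, may ask for individual codes, and can recommend a hold or stop without any count (12.4.7.3); the sponsor may stop for any reason.

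**Conclusion.** The point holds for the numeric stop in 7.5.2, on the literal list. Botulism is a named AESI that the count omits, while the breathing and swallowing components of the same syndrome are included. At the limit, one case entered only under the diagnosis turns a stop into a continue: four listed events plus one such case in the first 50 reads as four. That statement needs no assumed rate.

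The practical effect is very small. With 1% of qualifying cases entered that way, the chance of reaching the first limit falls by less than one percentage point at any rate considered. Even at 5% it falls by at most 4.7 points. These figures rest on assumed values of p and s and on one qualifying event per subject. Intensity and relatedness remain investigator judgements whichever terms are listed. This is a cheap improvement to a safety rule; it does not show that subjects are unprotected, and it does not extend to 7.5.1.

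**What to change.** In Protocol 7.5.2 only, add to the counted terms: Botulism, where the respiratory or swallowing involvement is itself severe, related to IP and lasts more than one week. Add one clause saying that a case entered both as Botulism and under one or more listed components is counted once. The qualifier keeps the addition within the scope of the existing rule.

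Leave 7.5.1 as it is. The limits of five in the first 50 and 10% thereafter do not change.

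The cost is one qualified term and one clause. No new visit or assessment is needed, since AESIs are already elicited at every post-injection visit, but someone must confirm that the involvement in a Botulism case meets the three conditions. The downside is a marginally more sensitive stop.
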